2	4/7/23	1. finished sentence in 17.2	no
3	4/10/23	1. updated sections 12.1 and 12.2 in protocol to reflect supporting documents	no
4	12/13/23	1. Updated recruitment information for pilot study to include new methods of recruitment (section 6.0) 2. Provided more general ingredients used in drink stimuli since we don't know which non-nutritive sweeteners will be used yet (that is the purpose of the pilot study), but all ingredients being tested are regularly available in the US food supply and have likely been consumed by nearly every participant. (section 7.1) 3. Removed blood pressure and BIA measurements since we no longer have this equipment available to use (section 8.2) 4. Changed timing of when dietary, physical activity, and health behavior questionnaires occur; also removed information about contacting lab personnel for opting out of further participation, as this is not needed or necessary when participants complete the questionnaires at a session in which they are	yes

1.0 Study Summary

Study Title	The impact of physiological response to sugar on brain activity and behavior
Study Design	This is a within-subjects study design. Results will be analyzed using linear regression and linear mixed effects models.
Primary Objective	The primary objective of this study is to study the effects of different types of sugars/carbohydrates commonly and abundantly found in the US food supply on metabolic rate, blood metabolites, and food reward.
Secondary Objective(s)	There are no secondary aims for this study.
Study Population	The general US population
Sample Size	20 for the pilot flavor tasting; 200 for the full study
Research Intervention(s)/ Investigational Agent(s)	Blood measurements, resting and post-consumption energy expenditure, questionnaires and ratings, fMRI
Study Duration for Individual Participants	Screening session: 2 hours In-Person Sessions: 3 sessions of 4 hours each, 12 hours total Online Sessions: 3 sessions of 15 minutes each, 45 minutes total Take-Home Drinks: 4 sessions of 5 minutes, 20 minutes total Post-test session: 3 hours
Acronyms and Definitions	fMRI, functional magnetic resonance imaging; FBRI, Fralin Biomedical Research Institute; CHBR, Center for Health Behaviors Research; SSB, sugar sweetened beverage; HNL, Human Neuroimaging Lab; ELISA, Enzyme linked immunosorbent assay

2.0 Objectives

2.1 Describe the purpose, specific aims, or objectives of this study:

The purpose of this study is to test the influence of different types of carbohydrates on metabolic response and food reward.

2.2 State the hypotheses to be tested:

For aim one, our hypothesis is that sucrose conditions greater appetitive effects than either fructose or glucose, its constituents, alone. For aim 2, our hypothesis is that fructose, incorporated into high fructose corn syrup, enhances the reinforcing properties of glucose, leading to more appetitive responses than sucrose paired with a non-nutritive sweetener, or sucrose alone.

3.0 Background

3.1 Summarize the relevant prior research on this topic and gaps in current knowledge within the field of study:

On any single day, 63-80% of people consume a sugar sweetened beverage (SSB), and in the US, adults consume ~46% of total added sugars in the form of SSBs. Beyond the established links with weight gain and increased adiposity deposition, excessive sugar intake is associated with reduced insulin sensitivity and may increase risk for type 2 diabetes. Fructose has independently been associated with increased intrahepatic lipid content and increased risk of non-alcoholic fatty liver disease. So, reducing SSB consumption could be an effective tool to reduce rates of obesity, type 2 diabetes, and nonalcoholic fatty liver disease. The assumption has been that oral sweet tastes drives SSB consumption; however, if sweetness alone drive consumption, the advent of "diet" drinks, which contain artificial sweeteners, would have driven substantially reduced SSB intake. This is not the case, and the exact reasons are unclear. We propose a potential underexplored mechanisms" engagement of post-oral/postingestive metabolic pathways that support behavior and preference that are not engaged by artificial sweeteners. Recent data indicated that post-ingestive signals of sugar availability may contribute to food reward and choice, and nutrients in the gut are able to rapidly change brain activity and influence food choice and behavior. These gut-brain circuits, however, are not well-understood. Furthermore, most of this work in understanding gut-brain connections has been performed in animal models; translating these findings to humans is necessary.

3.2 Describe any relevant preliminary data:

This is a new project without preliminary data collected.

3.3 Based on the existing literature, provide the scientific or scholarly rationale for and significance of your research and how will it add to existing knowledge:

Prior studies in humans indicate that while energy expenditure response is similar after consumption of equal amounts of fructose, glucose, and sucrose (a dimer of glucose + fructose), carbohydrate oxidation and blood glucose responses differ. Elevated carbohydrate oxidation responses appear to be driven by the presence of fructose, and elevated blood glucose responses appear to be driven by the presence of glucose. Prior work also suggests that post-ingestive signals of glucose availability, measure specifically as blood glucose levels, intestinal glucose transporter activity, and carbohydrate oxidation rate, are all associated with elevated brain response to calorie-predictive flavor cues and reward learning of these flavor cues. However, in animal models, glucose has been shown to repeatedly and reliably condition these calorie-predictive learning responses, but fructose does not. Human work has indicated that oxidation of glucose is critical for these responses. Thus, it is unclear what roles fructose and glucose each play in conditioning reward responses and flavor-calorie learning. We hypothesize that fructose plays a synergistic role in enhancing flavor-calorie learning without itself conditioning the reward response. We will test this hypothesis through this protocol.

4.0 Study Endpoints

*4.1 Describe the primary and secondary **study** endpoints. See links below for discussion of study endpoints and how they may differ from study objectives. These are most common in clinical trials but are sometimes applicable to other types of biomedical research, as well as social, behavioral, or educational research. See link below for a discussion.*

https://docs.google.com/document/d/1Wocz7K7a0hCQJPPO_khh5l1SQjhGDDGHzcOPRHR5Tw/edit?usp=sharing

Primary study endpoints are indirect calorimetry measurements, blood glucose measurements, beverage condition ratings and preferences (behavioral measures), and brain activation measured by fMRI.

*4.2 Describe any primary or secondary **safety** endpoints. These should be included for all studies that are greater than minimal risk. (Minimal risk: The probability and magnitude of harm or discomfort anticipated in the research that are not greater in and of themselves than those ordinarily*

encountered in daily life or during the performance of routine physical or psychological examinations or tests.):

There are no safety endpoints.

5.0 Study Design and Statistical Analysis Plan

5.1 *Describe the basic study design/approach (e.g., qualitative study using five focus groups of first year students to describe assimilation into the university community; randomized controlled trial of a behavioral change intervention to increase dietary intake of whole grains; pre- post-test evaluation of new pedagogical techniques to improve adult literacy):*

The pilot study will be a within-subjects design used to compare ratings of beverages with different levels of sweetness provided by different sugars and non-nutritive sweeteners (see 7.0:Investigational Agents: Beverage Solutions, below, for ingredients).

The overall study will be a within-subjects (crossover) design used to compare behavioral (beverage ratings and preferences), metabolic (blood glucose & metabolites, indirect calorimetry measures), and brain activation responses (fMRI) to glucose-, fructose-, and sucrose-containing beverages (Aim 1); and sucrose-, high fructose corn syrup (HFCS)-, and non-nutritive sweetener + sucrose- containing beverages (Aim 2).

5.2 *Describe corresponding data analysis plan/approach (e.g., content analysis of focus group transcripts; descriptive analysis followed by linear regression modeling; nonparametric analysis of pre- and post-test measures):*

Linear mixed effects models will be used to assess the following outcome variables: change in indirect calorimetry measures, change in blood glucose and insulin, change in beverage liking. Linear regression will be used to relate blood and indirect calorimetry measures to liking and other subjective ratings.

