8.0 Procedures Involved

8.1 *Describe and explain the study design:*

This is a within-subject analysis plan where participants receive at least 3 beverages and undergo blood draw, indirect calorimetry measurements, and an MRI scan.

8.2 *Provide a description of:*

- *All research procedures being performed*
- *If the study has more than one procedure, session, and/or subject population, describe each procedure, session, and/or study population separately. For complex studies, you are encouraged to include a figure or chart.*

PILOT STUDY:

Overview

The sugars and non-nutritive sweeteners will be using in our full study all have different levels of sweetness due to their chemical structures. To decide what amounts of each of these to use, we will conduct a) pilot study, in which a convenience sample of participants (~20) will taste and rate a variety of mixtures of sugars and non-nutritive sweeteners. To reduce the potential for "tasting fatigue," only a limited number of mixtures will be tasted during a single 2-hour session, but participants will be allowed to complete as many pilot study sessions as they choose.

Recruitment

A convenience sample of participants will be recruited primarily via word-of-mouth or email from our lab's Ripple database (see section 9.4 for information about Ripple). Emails will be generated for individuals who opted-in to contact about participation in future studies with our lab when they filled out a screening survey. See supporting documents for email wording.

[figure not shown]
Informed Consent

Participants will be sent via email the consent form for the study at least 24 hours in advance of their scheduled consent session. Upon arrival for the session, participants will have ample time to review and sign the consent form prior to beginning the training session. Research personnel will be available to answer any questions the participant may have.

Flavor and Sweetness Ratings

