CONSENT SESSION (Called "pretest" in study design figure above) (~2.5 hours):

Informed Consent

Participants will be sent via email the consent form for the study at least 24 hours in advance of their scheduled consent session. Upon arrival for the session, participants will have ample time to review and sign the consent form prior to beginning the training session. Research personnel will be available to answer any questions the participant may have.

Anthropometrics and Clinical Measures

Participants' height, weight, hip circumference, and waist circumferences will be measured. Height will be measured using a stadiometer, weight using a body weight scale, and waist and hip circumference using a standard Gulick tape measure. A fingerstick blood sample will be collected for point-of-care hemoglobin A1C assessment to ensure eligibility. A lancing device and single-use lancet will be used to obtain a finger stick. A point-of-care A1C analyzer and appropriate cartridges will be used to assess hemoglobin A1C.

Flavor Ratings

The participants will first be trained by the researcher on how to use the standard perceptual rating scales. Then participants will taste and make ratings of beverages using the standard rating scales. After the participant has completed the tasting protocol, the researcher will determine three flavors to be used in the beverages the participants will consume during the behavioral conditioning sessions.

Mock MRI Training

Participants will also complete a "mock" MRI training, in which they learn to swallow small amounts of liquids while lying supine. (Note: most people have no difficulty learning to swallow small quantities of liquid while lying down). This training will be performed in an MRI simulator that is the same bore size and similar environment to the real scanner, but does not contain a magnetic field. Participants who have difficulty with supine swallowing or who express discomfort in the simulated fMRI environment may be excluded from the study or only undergo portions of the study that do not involve fMRI scanning. If not completed during the consent session, participants will be asked to complete this training as part of another conditioning session. Compensation for this "mock" scan is built into the compensation for the consent session.

Dietary Intake

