Participants will rate their hunger, thirst, and fullness on standard visual analog scales while fasted and after consumption of the beverage, along with perceptual ratings about the beverages consumed during the session.

IV Blood Draws

An IV catheter will be inserted into the participant's arm for venous blood draws throughout the session. This catheter will remain in the participant's arm for the duration of the session (~4 hours). A fasting baseline draw will be made, and then six additional blood draws after the participant consumes the conditioning beverage will be conducted throughout the remaining session. Two tubes of no more than 5 ml each will be collected at each blood draw (14 tubes total). This is approximately 126 ml of blood in total (~8-9 tablespoons). This is roughly equivalent to 1/4 the amount of blood given during a typical blood donation. All blood draws will occur while the participant is reclining on a bed inside a metabolic chamber (see Metabolic Chamber Indirect Calorimetry below). For the draws, the researcher performing the blood draws will reach their arms into the chamber via ports on the side of the chamber walls. Participants will be able to communicate with research personnel using a 2-way intercom system, and the walls of the metabolic chamber are clear plexiglass that allow researchers and participants to see each other throughout the measurement. IV blood draws occur concurrently with metabolic chamber measurements (see below). The IV catheter line will be flushed with normal saline between each blood draw to prevent coagulation in the catheter tubing. After the final blood draw, the catheter will be removed and the venipuncture site secured with sterile tape or bandage. Should the IV catheter placement fail or become unusable during the session, the catheter will be removed and participants will continue with the metabolic chamber indirect calorimetry portion of the session.

Metabolic Chamber Indirect Calorimetry

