Participants will rest reclined on a bed inside the metabolic chamber for the duration of the measurement. The chamber is an open-circuit system in which fresh air is pumped into the room at a specified flow rate. Metabolic chamber measurements involve non-invasive collection and measurement of oxygen and carbon dioxide concentrations expired through respiration. Metabolic chamber measurements occur concurrently with IV blood draws (see above). Participants will be able to communicate with research personnel using a 2-way intercom system, and the walls of the metabolic chamber are clear plexiglass that allow researchers and participants to see each other throughout the measurement. A fasting measurement will be collected for approximately 30-60 minutes; during this time a fasting blood draw will also be collected (see IV Blood Draws above). After the fasting measurement, participants will consume the conditioning beverage, and a post-beverage measurement will be collected for approximately 3 hours.

Beverage Consumption

Participants will consume the single 355 ml, 110 kcal conditioning beverage within 5 minutes. The conditioning beverage contains flavoring, citric acid (commonly used in sugar-sweetened beverages [e.g., Gatorade]), deionized water, and the sugar or sugar + non-nutritive sweetener stimuli being tested. Participants will rate their hunger, thirst, and fullness on standard visual analog scales after consumption of the beverage, along with perceptual ratings about the beverages consumed during the session.

Take-Home Beverages

At the end of the session, participants will be provided 5 bottles of the same conditioning beverage to be consumed at home. One bottle will be used for the at-home conditioning session (see below), and the remaining 4 total bottles will be consumed at the following times: 1 hour before dinner the same day as the in-person and at-home conditioning sessions (1 bottle for each conditioning session), and 1 hour before lunch the day following the in-person and at-home conditioning session (1 bottle for each session).

AT-HOME CONDITIONING SESSIONS (~15 minutes each, 45 minutes total):

Fast and Refrain from Exercise

Participants will be asked to refrain from exercise for at least 24 hours and fast for at least 3 hours prior to each conditioning session.

Consumption of Planned Breakfast Meal

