Participants will be instructed to consume the same breakfast meal the morning of each at-home conditioning session. They will have planned this meal with research personnel during the consent session. They will be responsible for procuring and/or preparing these meals at home. They will be instructed to consume only plain water after finishing this meal until their scheduled conditioning session time.

Zoom Monitoring of Consumption

A Zoom link will be sent to the participant prior to the scheduled at-home conditioning session time. During the session, participants will turn their camera on to allow the

researcher to watch them drink the conditioning beverage. This session will NOT be recorded. At the end of the session, participants will be reminded to consume the take-home beverages at the appropriate specified times: 1 hour before dinner the same day, and 1 hour before lunch the following day. Participants will be sent an automated email with a link to a REDCap survey. Participants will rate their hunger, thirst, and fullness on standard visual analog scales before and after consumption of the beverage, along with perceptual ratings about the beverages consumed during the session on this survey.

TAKE-HOME BEVERAGE CONSUMPTION (~5 minutes each, 60 minutes total):

Consumption of Planned Breakfast Meal

Participants will be instructed to consume the same breakfast meal the morning of each lunch beverage consumption time. They will have planned this meal with research personnel during the consent session. They will be responsible for procuring and/or preparing these meals at home. They will be instructed to consume only plain water after finishing this meal until their scheduled lunch beverage consumption time.

Consumption of Take-Home Beverages

Participants will be instructed to consume the take-home beverages 1 hour before dinner the same day as their conditioning session (either in-person or at-home; see above) and 1 hour before lunch the day following their conditioning session (either in-person or at-home). Participants will be sent surveys to verify beverage consumption times and amounts via REDCap. These surveys will be sent using the automated invitation function in REDCap, which will generate an email containing unique links for each survey for each participant. Only participant email addresses will be stored as participant identifiers to track survey responses for data collection.

POST-TEST SESSION (~3 hours):

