Fast and Refrain from Exercise

Participants will be asked to refrain from exercise for at least 24 hours and fast for 3 hours prior to each conditioning session.

Internal State Ratings

Participants will rate their hunger, thirst, and fullness on standard visual analog scales while fasted and periodically throughout the session.

Flavor Ratings

Participants will taste and make ratings of flavored beverages using standard rating scales. These are the same beverages and flavors used throughout the study.

MRI Scan

The MRI scan will occur at the Human Neuroimaging Laboratory at FBRI. MRI safety will be reviewed with the participant by an FBRI-approved scanner operator prior to entering the scanner room containing the magnet. Participants and experimenters will remove metal from their bodies and clothing (e.g., jewelry, cell phones, coins, etc.). Participants will also complete an MRI safety form to ensure they qualify to have an MRI performed (included in supporting documents). Prior to entering the scanner room with

the magnet, experimenters will use a metal detection wand to scan over the participant to ensure no metal that could be subject to the magnet's pull is detected (e.g., zippers or grommets on clothing cannot be pulled off by the magnet). Inside the scanner room, participants will lie on a table that slides into the bore of the scanner. Using a head coil, functional images will be acquired using an EPI bold sequence. Participants will wear disposable earplugs and other ear protection to minimize the amount of noise heard during the scan (magnetic field gradient changes during the scan can be loud).

Participants are able to communicate with the experimenter via either a speaker and microphone system (between scanning segments) or with an emergency squeeze ball (during scan acquisition). Participants will be instructed to talk with experimenters between scanning segments via microphone-and-speaker system and to use the squeeze ball during scan acquisition for emergencies (e.g., they begin to feel claustrophobic during the scan). The experimenters will check in with participants periodically between scanning segments to ensure participant comfort.

Scanner Taste Tasks

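### Does the undefined baseline for the change in beverage liking leave that outcome unable to separate learning from taste?

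*Combined protocol and SAP*

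**What the plan says.** Section 4.1 places beverage ratings and preferences among the primary endpoints and gives no time point. Section 5.2 names the modelled outcomes in one line: "change in indirect calorimetry measures, change in blood glucose and insulin, change in beverage liking". It adds neither time points nor a description of the drink that is rated.

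Section 8.2 describes four kinds of rating occasion.

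- **Consent session**, labelled the pretest in the design figure: "Then participants will taste and make ratings of beverages using the standard rating scales". Then: "After the participant has completed the tasting protocol, the researcher will determine three flavors to be used in the beverages the participants will consume". Sweetener content is not stated.
- **In-person conditioning session**: hunger, thirst and fullness are rated fasted and after the drink, "along with perceptual ratings about the beverages consumed during the session". The Beverage Consumption paragraph puts these ratings "after consumption of the beverage, along with perceptual ratings about the beverages consumed during the session".
- **At-home conditioning session**: internal states are rated "before and after consumption of the beverage, along with perceptual ratings about the beverages consumed during the session on this survey".
- **Post-test session**: flavoured beverages are tasted and rated, and "These are the same beverages and flavors used throughout the study".

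Three other places bear on the point. The Beverage Consumption paragraph describes the conditioning drink (355 ml, 110 kcal, with flavouring, citric acid, deionized water and the sweetener under test). The pilot overview says that the sweeteners differ in sweetness, and gives this as the reason for the pilot: "To decide what amounts of each of these to use, we will conduct". Sections 14.1 and 14.3 require flavours that a participant finds equally liked and equally unfamiliar, and 14.3 places that judgement in the consent session.

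**The concern.** The hypotheses in sections 2.2 and 3.3 are about conditioning and flavour-calorie learning, and section 3.1 sets post-ingestive signals against oral sweetness. A liking outcome that also picks up the immediate taste of each sugar would blur the distinction the study is built to examine.

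Three readings of the change in liking fit the text:

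1. Post-test minus pretest, where the test sweetener is in the post-test drink only.
2. Post-test minus pretest, with the same composition at both times.
3. Post-test minus a rating from the week in which each drink was consumed.

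Reading 1 adds a taste difference to the learning contrast. Reading 3 removes taste, but its baselines in weeks 2 and 3 follow other drinks with no washout. An outcome left open in this way could also, in principle, be settled after the data are seen. For a primary behavioural endpoint, that looks like a gap that ought to be closed.

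**Working it through.** **The plan's own figure.** Section 14.1 wants 70 completers in each aim, 140 in all, and expects about 30% loss. 140 / (1 − 0.30) = 200, which matches the number to be consented. The 70 itself cannot be reproduced, because no alpha, power, effect size or SD is given. The point at issue does not depend on it.

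**What each reading estimates.** For a drink d, let f be liking of the flavour alone, s the immediate effect of the sweetener on liking, and L the learned change. For two drinks A and B:

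- Reading 1: pretest = f, post-test = f + s + L. The contrast in change is (s_A − s_B) + (L_A − L_B).
- Reading 2: pretest = f + s, post-test = f + s + L (or f and f + L in a common vehicle). The contrast is L_A − L_B.
- Reading 3: the own-week baseline also contains s, so taste cancels and carryover becomes the issue.

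The readings therefore do have different targets.

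**Size under reading 1.** All inputs except n are assumed: n = 70, rating SD 1, correlation 0.5 between the two ratings, two-sided 5%, zero learning.

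- SD of one drink's change = √(2 × (1 − 0.5)) = 1.
- SD of the difference in change between two drinks = √2.
- Taste difference 0.25: dz = 0.25/√2 = 0.177, rejection 0.31 (noncentral t).
- Taste difference 0.50: dz = 0.50/√2 = 0.354, rejection 0.83.

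An opposite taste difference could equally hide real learning. In a simulation with a taste offset of −8 points and learning of +8 points, reading 1 estimated 0.0. The documents give no taste difference or SD, so none of this measures bias in this trial.

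**Does one reading clearly win?** Suppose carryover c comes from drink A only and affects the drink that directly follows it. Orders are balanced, and A directly precedes B in 2 of the 6.

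| Carryover | Reading 2, A − B | Reading 3, A − B |
|---|---|---|
| From A only, gone by post-test | 0 | +c/3 |
| From A only, persisting to post-test | −c/3 | 0 |
| Same from every drink | 0 | 0 |

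With c = 1 SD the bias is 0.33 in whichever reading is affected. Simulated rejection was 43% for reading 3 in the first row and 41% for reading 2 in the second. The ranking reverses with an assumption on which the documents are silent. Carryover common to all drinks falls equally on each drink across balanced orders and drops out of the contrast, so only carryover that differs between drinks matters.

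Reading 2 is also not the only route to the learning contrast. Rating the flavours in a common vehicle at post-test alone, with flavour-sugar pairing randomised, gave 0.0 and about 5% rejection under zero learning.

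**Which reading do the documents point to?**

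- The sessions are labelled pretest and post-test.
- Sections 14.1 and 14.3 tie liking to the consent session, where flavours are selected for equal liking.
- The conditioning-session paragraphs speak of perceptual ratings and do not name liking, so reading 3 has little direct support.
- The post-test paragraph says its drinks are those used throughout, which settles their composition and leans towards like-with-like comparison.

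What stays open is the sweetener content of the pretest drinks.

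**The case for a change.** The strongest case for a change is that reading 1 is realistic. The three flavours are fixed only after the pretest tasting, so the final pairings of flavour and sugar do not exist when those ratings are made. Unless candidates were tasted in each test sweetener, or in a vehicle used again at post-test, the compositions differ. The post-test sentence does not settle what was poured at pretest. The pilot paragraphs speak of acceptable concentrations and state no rule for matching sweetness. One sentence in the SAP might be enough.

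Most of that stands as a description of the gap, but it does not show that a biased comparison is planned. The text neither intends nor excludes reading 1, and the design figure that might settle it is not available here.

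If more than a sentence were needed, the remedies are debatable. Tasting each sweetened drink at the consent session adds exposure to flavours that are meant to be unfamiliar. A common vehicle may carry only part of the learned liking: if half of a 0.5 SD effect transferred, power would fall from 83% to 31% on the values assumed above. Nor would either step separate post-ingestive learning from learning driven by sweetness, because repeated pairing with a sweeter taste can itself change liking.

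The worry about choosing the definition afterwards supposes that liking is rated on all four occasions, which the text does not say. Nothing in the documents suggests such selection.

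**Conclusion.** The gap is real and narrow: section 5.2 does not name the ratings that form the change in liking, and the pretest drinks' sweetener content is not in the readable text. It does not call for a change to the plan. The surrounding sections point to a pretest-to-post-test comparison, the post-test drinks are identified, and analysts who know what was poured at pretest can be expected to compare like with like.

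The size of any bias is unknown. The 31% and 83% figures apply only if compositions differ, a taste difference of 0.25 or 0.5 SD survives the pilot, and the assumed SD and correlation hold. No alternative is clearly better: own-week and pretest baselines swap places according to whether carryover persists, and the two tasting remedies trade one weakness for another. This conclusion rests on the readable text alone. A design figure or tasting procedure showing different compositions at the two times would make the taste component a live issue.
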